7.1. Informed Consent

The Investigator will provide for the protection of the patients following all applicable Good Clinical Practice (GCP) regulations. The informed consent form (ICF) must be reviewed and approved by the Sponsor and the Institutional Review Board (IRB)/ Independent Ethics Committee (IEC) before the informed consent process may begin.

Prior to performing any study-specific screening or study-related procedures for any potential patient to be enrolled, the patient must be given or must complete the following:

- Be informed of all pertinent aspects of the study and all elements of informed consent
- Be given time to ask questions and time to consider the decision to participate
- Voluntarily agree to participate in the study
- Sign and date an IRB/IEC approved Informed Consent Form

Study personnel must obtain documented consent from each potential patient prior to entering in a clinical study. Consent must be documented by obtaining the dated signature of both the patient and the person conducting the consent discussion on the consent form. If local law does not allow written consent, then oral consent, attested to by the dated signature of an impartial witness (someone not involved with the conduct of the study), is the required alternative.

If the patient is illiterate, an impartial witness must be present during the entire informed consent reading and discussion. Afterward, the patient should sign and date the informed consent, if capable. The impartial witness should also sign and date the informed consent along with the individual who read and discussed the informed consent (ie, study staff personnel). If the patient is legally incompetent (ie, mentally incapacitated), the written consent of a legal guardian or legal representative must be obtained. Depending on local law or review committee requirements such consent may also need to be signed by an impartial witness.

The information from the consent form should be translated and communicated to the patient in language understandable to the patient. When the study patient population includes non-English speaking people, a certified translated consent form or an appropriate equivalent will be provided to the patient.

The initial informed consent form and any subsequent revised written informed consent form must receive approval and/or favorable opinion by the IRB/IEC in advance of use. The patient or his/her legally acceptable representative should be informed in a timely manner if new information becomes available that may be relevant to the patient's willingness to continue participation in the study. The communication of this information should be documented.

A copy of the signed ICF will be provided to the patient. The Investigator will retain all original versions of signed ICFs.

After informed consent is provided, patients who successfully complete all screening assessments and study entry criteria may be enrolled in the study. The period for completing screening assessments is 28 days.

An optional supplemental consent for future use of blood and tissue samples for research purposes (biobanking) may be proposed to patients based on local regulatory requirements. The assessments to be conducted on these samples are described as exploratory endpoints in the protocol.

Rescreening of patients is only allowed once per patient if the patient is not registered as entering the treatment phase (Cycle 1 Day 1). In this case, a new patient number will be assigned, and the patient will be identified with this number throughout their participation in the study.

7.2. Screening Period

Selected screening procedures are highlighted below. A summary of all screening assessments to be performed is provided in the Schedule of Events (Table 11).

7.2.1. Demographic Information

Standard demographic parameter information including age, gender, and race/ethnicity (recorded in accordance with local regulations) will be collected at the screening visit.

7.2.2. Physical Examinations

Physical examinations will be performed as specified in the Schedule of Events (Table 11). Documentation of the physical examination will be included in the source documentation at the investigational site. Any changes from the screening physical examination findings that meet the definition of an AE must be recorded on the AE eCRF.

7.2.3. Medical History

All relevant cancer-related history over the patient's lifetime should be recorded, including:

- Initial diagnosis
- Prior antineoplastic therapies (including surgery and radiotherapy) and dates
- Responses to prior antineoplastic therapies

The non-cancer-related medical history should include any ongoing medical conditions and symptoms and should also include the toxicity grade NCI CTCAE Version 5.0.

7.2.4. Tumor Specimen

An FFPE tumor block or 10 unstained slides of a representative tumor specimen obtained ≤2 years prior to screening must be available and submitted to the central pathology laboratory within 8 weeks after Cycle 1 Day 1. For available tumor specimens >2 years old, the Sponsor's Medical Monitor should be consulted to discuss eligibility.

The specimen must be representative of the current disease. If archival tumor tissue (tumor block or unstained slides) was not available prior to enrollment, a newly obtained tumor biopsy (excisional or core) may be required prior to enrollment. If a new biopsy is obtained to satisfy

eligibility, an FFPE tumor sample should be provided to the central pathology lab. De-identified pathology reports associated with these tissues are also required and must be sent to the central pathology laboratory with the tissue and/or slides.

The process for submitting archived tissue and procedures for central pathology review is provided in a separate Study Manual.

7.2.5. Baseline Disease Assessments

Any imaging assessments already completed during the regular work-up of the patient within 21 days prior to Cycle 1 Day 1, including before signing the main study ICF, can be considered as the baseline images if all imaging requirements for the study are met.

The imaging modality used for evaluation at screening must be consistently used throughout the study for each patient (CT with contrast or MRI). If positron emission tomography (PET) is used, a contrast-enhanced CT scan must be included.

7.2.6. Eligibility Determination and Patient Registration

Investigative sites will submit patient registration materials for Sponsor's Medical Monitor approval prior to the enrollment of the patient in the trial. Details on this process will be included in the Study Manual.

Once all screening procedures are complete, an eligibility checklist must be completed by the Investigator or designee and provided to the Sponsor's Medical Monitor with limited exceptions at least 72 hours prior to planned enrollment for review. Eligibility will be reviewed and approved by the Sponsor Chief Medical Officer or designee (eg, Sponsor's Medical Monitor) prior to patient enrollment.

7.2.6.1. Screen Failures

Patients who sign an ICF but are later deemed to be ineligible for enrollment before taking any study medication will be considered screen failures. The eCRF completion requirement for screen failures is outlined in the eCRF Completion Guidelines.

7.3. Treatment Period

Patients will be treated until discontinuation of study treatment as described in Section 7.3.3.

7.3.1. Treatment Cycles

Patients will receive nanatinostat at the assigned dose once or as a divided dose twice daily on Days 1 to 4 per week or Days 1 to 7 per week and valganciclovir 900 mg orally once daily, twice daily (for 21 days, with a subsequent dose reduction to 900 mg daily), or 450 mg orally twice daily continuously for 21-day treatment cycles (excluding Cycle 1, which is 28 days).

Pembrolizumab (200 mg IV) will be administered every 3 weeks starting on Cycle 1 Day 8.

7.3.2. Unscheduled Visit(s)

Unscheduled visits will be recorded in the eCRF. The specific tests and evaluations performed during an unscheduled visit will be determined by the Investigator.

7.3.3. Discontinuation of Study Treatment

Patients will continue study treatment until disease progression, unacceptable toxicity, start of new anti-neoplastic therapy, withdrawal of consent by the patient, patient is lost to follow-up, or discontinuation from the study due to any other reason (eg, Sponsor terminates the study). Maximum treatment duration with pembrolizumab is 24 months.

In case a patient voluntarily discontinues from study treatment, the Investigator must make every effort to determine the primary reason for the decision and record this information in the eCRF.

If a patient withdraws consent for participation in the study, all data collected up to the point of withdrawal must be maintained in the database and included in subsequent analyses, as appropriate. A patient may withdraw from the interventional portion of the study, but agree to continue follow-up of associated clinical outcome information in which case this information would be collected and maintained in the clinical trial database.

Patients who discontinue treatment without relapse/disease progression will continue to follow the CT scan assessment schedule until disease progression, start of new anti-neoplastic therapy, withdrawal of consent, completion of one year of follow-up, lost to follow-up, or end of study (see Table 11), whichever comes first.

Patients may be withdrawn permanently from the study if any of the following occur:

- Adverse event
- Progressive disease or relapse per RECIST v1.1 or iRECIST (for patients receiving pembrolizumab only)
- Lost to follow-up
- Physician decision
- Pregnancy
- Withdrawal of consent
- Study terminated by Sponsor
- Any protocol deviation for which continuing participation in the study would result in a significant risk to the patient's safety

7.3.4. End of Treatment

At the time patients discontinue study treatment, a visit should be scheduled as soon as possible and within 14 days after the last dose of study drug, at which time all assessments listed for the End of Treatment (EOT) visit will be performed. The EOT visit will be recorded in the eCRF with the date and reason for stopping the study treatment. At a minimum, all patients who discontinue study treatment, including those who refuse to return for a final visit, will be contacted for follow-up safety evaluations 30 and 90 days following the last dose of study drug(s).

The assessments to be performed at EOT are listed in the Schedule of Events provided in Table 11.

7.3.5. Safety Follow-up Visit

All patients must complete safety follow-up assessments at 30 (\pm 5) and 90 (\pm 5) days following the final administration of study treatment. If a patient withdraws consent after the EOT visit but prior to the 30-day safety evaluation, safety information should be collected on the patient up to the date of consent withdrawal. The 90-day safety follow-up assessments may coincide with the first Long-Term Follow-up visit.

For each safety follow-up assessment, the following should be collected:

- 30-day Safety Follow-up:
 - AEs
 - Prior/concomitant meds for AEs
 - Pregnancy testing (for women of childbearing potential)
 - EBV DNA levels
 - Any antineoplastic therapies
- 90-day Safety Follow-up:
 - AEs (for the Phase 2 patients receiving pembrolizumab)
 - SAEs (for all patients)
 - Prior/concomitant meds for AEs
 - Any antineoplastic therapies

AE information will be collected following the last dose of study treatment through the appropriate safety follow-up period described above or until the start of a new antineoplastic therapy, whichever occurs first.

In addition to AEs, all concomitant medications given to a patient because of an AE during this period will be recorded on the Prior and Concomitant medication eCRF page.

All new anti-cancer therapies given to a patient within 90 days after the last dose of study treatment must be recorded in the eCRF. If a new antineoplastic treatment is initiated before the 30-day safety evaluation, safety follow-up will occur immediately before starting the new treatment. If a patient withdraws consent after the EOT visit, but prior to the 30-day safety evaluation, safety data should be collected on the patient up to the date of consent withdrawal.

7.3.6. Long-term Follow-up Visits

The first Long-Term Follow-up visit may coincide with the 90-day safety follow-up assessment.

Patients who discontinue treatment for reasons other than disease progression will have tumor imaging and plasma EBV DNA level assessments every 12 weeks $(3 \text{ months}) \pm 7 \text{ days}$ as detailed in Table 11, for up to 1 year following the last dose of study drug treatment, until disease progression, the start of subsequent anti-cancer therapies, withdrawal of consent, lost to follow up, or end of study, whichever occurs first. Scans performed during the Follow-up period should be performed on the same schedule with the same imaging modality as previously used throughout the study.

Survival Follow-up: All patients enrolled in the study will be followed for survival every 12 weeks (3 months) by phone call, e-mail, medical records, clinic visits, or public records, such as government census or death records, until the patient is lost to follow-up, death, withdraws consent, completion of 3 years of follow-up, completion of 1 year after the last patient discontinues study treatment, or the study is terminated by the Sponsor, whichever occurs first. Newly started anti-neoplastic therapies during this follow-up period must be recorded on the "Antineoplastic therapies since discontinuation" eCRF page.

7.3.7. Lost to Follow-up

Patients who do not complete scheduled visits and who are unable to be contacted following at least 3 documented attempts (one of which is contact by certified/registered mail) will be considered lost to follow-up.

7.4. Assessments During the Treatment Phase

Study treatment will start on Cycle 1 Day 1. Serial assessments of safety and efficacy will be performed as outlined in the Schedule of Events provided in Table 11. On scheduled visit days, the use of the central laboratory is preferred for all protocol-specified laboratory analyses; however, additional local laboratory assessments may be performed, as applicable, per site policy or for unscheduled visit days. Clinical decisions and dose modifications can be based on local laboratory results.

7.4.1. Efficacy Assessments

7.4.1.1. Baseline Evaluation

The following radiologic assessments are to be performed in the screening period (within 21 days prior to the start of treatment):

- 1. For all patients: CT with contrast or MRI of the head to rule out CNS involvement.
- 2. **For NPC patients:** CT with contrast or MRI of the nasopharynx, neck, chest, abdomen, and pelvis. If PET is used, a contrast-enhanced CT scan must be included.
- 3. For non-NPC patients: CT with contrast or MRI of the chest, abdomen, and pelvis.

7.4.1.2. Tumor Response Assessments

Tumor responses will be assessed by the Investigator per RECIST v1.1 (MRI or CT with contrast) and iRECIST (for patients receiving pembrolizumab). The CT scans should be performed with contrast unless contraindicated for medical reasons, in which case MRI should be used.

Although RECIST v1.1 will be the primary measure for assessment of tumor response and disease progression for efficacy endpoints, iRECIST guidelines should be used for treatment decision making for patients receiving pembrolizumab, including confirmation of unconfirmed progressive disease by RECIST v1.1 with additional imaging within 4 to 6 weeks (Appendix 3).

Investigator-determined response assessments at each assessment time point will be entered into the appropriate eCRF. Copies of all scans and redacted radiology reports are to be submitted according to vendor / Sponsor requirements in a timely manner.

All MRI or CT scan assessments will be determined from date of first dose and will follow the counting of calendar days and not the dosing cycles. It is critical that the same imaging modality used at screening is used throughout the study for each subject. The scans will be performed as follows:

- At Week 8 and then every 6 weeks (±7 days) for the first 26 weeks (6 months), and every 12 weeks thereafter for up to 1 year after permanent discontinuation of study treatment, until disease progression, the start of new anti-cancer treatment, withdrawal of consent, lost to follow-up, or the end of the study, whichever occurs first. A scan to confirm an unconfirmed PR or unconfirmed CR ≥4 weeks later may also be performed.
- At the EOT visit (unless the previous scan is within 4 weeks of the EOT visit).

If local regulatory authorities mandate less frequent imaging, the minimum frequency must be every 12 weeks.

All patients will be followed for disease progression or relapse using the schedule described in the Schedule of Events provided in Table 11. This includes patients who discontinue the protocol-specified treatments or the study early for any reason without documented evidence of progressive disease or relapse.

The radiologic assessments (MRI or CT with contrast) are considered the primary method of response assessment.

Patients who relapse or progress will continue to be followed for OS, all subsequent antineoplastic therapy, and response, including disease progression/relapse to subsequent antineoplastic therapy.

For a patient receiving pembrolizumab deemed clinically stable at the time of initial progression by RECIST v1.1, Investigators may elect to keep the patient on treatment using the iRECIST guidelines to assist with patient management (Appendix 3). Tumor imaging should be repeated within 4 to 6 weeks to confirm disease progression using iRECIST. Patients who have confirmed disease progression per iRECIST will discontinue treatment unless continued treatment is approved by the Sponsor.

7.4.2. Safety and Tolerability Assessments

Study assessments of safety include AEs, clinical laboratory tests, ECGs, vital signs, physical examinations, and ECOG status.

Safety data will be collected from the signing of the ICF up to and including 90 days post-last dose of study treatment according to the Schedule of Events in Table 11.

Adverse event monitoring and collection, in addition to other safety considerations, are summarized in Section 8. Laboratory assessments, vital signs, ECGs, physical examinations, and ECOG performance status are described in the subsequent sections below.

Tolerability will be assessed by the incidence of AEs leading to dose modifications or study drug discontinuation.

7.4.2.1. Laboratory Evaluations

7.4.2.2. Clinical Laboratory (Safety) Testing

Laboratory tests will be collected and analyzed in an accredited central or local/site laboratory in accordance with quality standards.

On scheduled visit days, the use of the central laboratory is preferred for the analysis of all indicated safety laboratory analyses; however, local laboratory assessments may be performed, as applicable, per site policy or for unscheduled visit days. Clinical decisions and dose modifications can be based on local laboratory results.

The required hematology, serum chemistry, urinalysis, serology, and other parameters to be collected at the time points described in the Schedule of Events (Table 11) are listed in Table 12. These tests may also be performed when clinically indicated (eg, patients who are hepatitis B core antibody positive should have HBV DNA PCR monitoring according to local guidelines). In addition, the investigative sites will provide archived and/or newly obtained tumor samples at baseline, and at Cycle 1 Day 15 and/or at the time of relapse or with disease progression, as applicable.

Viral levels (EBV, CMV, and HIV [for HIV⁺ patients only]) will also be monitored to assess for viral reactivation.

Table 12: Required Laboratory Tests

Laboratory Test Category	Laboratory Tests						
Hematology	Hemoglobin, platelets, WBC with differential (absolute neutrophils, absolute monocytes, absolute eosinophils, absolute lymphocytes, absolute basophils),						
Coagulation	PT or INR, aPTT						
Serum Chemistry	AST (SGOT)	Bicarbonate					
	ALT (SGPT)	BUN					
	Albumin	Creatinine					
	Total bilirubin	Glucose (non-fasting)					
	Sodium	Chloride					
	Potassium	Calcium					
	Magnesium	Phosphate					
	Total protein	Uric acid					
	ALP	Thyroid function tests (TSH, free T3, free T4)					
Urinalysis	Macroscopic panel (dipstick)						
Viral	HBV surface Ag	HBV DNA PCR ¹					
	HBV core and surface Ab	HCV Ab ²					
	EBV DNA, CMV, HIV levels						
Pregnancy	Only for females of childbearing potential. Serum test must be performed during screening. Serum or urine tests are to be performed as described in the Schedule of Events. Pregnancy tests will be performed locally at each site.						

¹HBV DNA PCR only for patients with positive HBV core Ab or surface Ag.

Ab = antibody; Ag = antigen; ALT = alanine aminotransferase; aPTT = activated partial thromboplastin time; ALP = alkaline phosphatase; AST = aspartate aminotransferase; BUN = blood urea nitrogen; CMV=cytomegalovirus; EBV = Epstein-Barr virus; HBV = hepatitis B virus; HCV = hepatitis C virus; HIV = human immunodeficiency virus; INR = international normalized ratio; PCR = polymerase chain reaction; PT = prothrombin time; SGOT = serum glutamic-oxaloacetic transaminase; SGPT = serum glutamic-pyruvic transaminase; TSH = thyroid stimulating hormone; WBC = white blood cell.

7.4.2.3. Pregnancy Testing

Pregnancy testing is only required for females of childbearing potential. A serum test must be performed during screening. Serum or urine tests are to be performed at the beginning of each cycle, at EOT, at the 30-day Safety Follow-up visit, and for up to 6 months post-last dose of study treatment. Pregnancy tests will be performed locally at each site.

7.4.2.4. Vital Signs

Vital signs (temperature, blood pressure, and heart rate) will be collected at the screening visit (Day -28 to Day -1), on Day 1 of each cycle, and at the EOT visit. For Phase 1b dose levels 1 through 7, vital signs should be collected just prior to the first dose of valganciclovir and nanatinostat, and in concert with and just prior to PK blood draws on Cycle 1 Day 1 and Cycle 2 Day 1 through the 6-hour post-dose time point. For Phase 1b dose levels 8 through 13 and Phase 2, vital signs should be collected just prior to the first dose of valganciclovir and nanatinostat, and in concert with and just prior to PK blood draws on Cycle 2 Day 1 through the 6-hour post-dose timepoint as shown in Table 11. On other indicated visit days, vital signs will be collected once (prior to dosing of study treatment, if administered in clinic).

Investigators are to report any clinically significant abnormal findings as AEs.

²Any patient positive for HCV Ab will be evaluated by quantitative PCR.

7.4.2.5. Cardiac Assessments: Electrocardiograms (ECGs)

All 12-lead ECGs will be conducted in triplicate. Average QTcF will be calculated to confirm eligibility. ECG tracings will be provided to a central laboratory, instructions are provided in the Study Manual.

Triplicate 12-lead ECGs will be performed separated by approximately 1 minute at screening, on Cycle 1 Day 1 (Phase 1b, all dose levels, and Phase 2), Cycle 2 Day 1 (Phase 1b dose levels 8 through 13 and Phase 2 only) and at the EOT visit. Average QTcF will be calculated to confirm eligibility. Careful skin preparation is essential to assure high quality ECGs. All ECGs should be collected using the same ECG machines and performed in as calm an environment as possible, not immediately following stressful procedures (ie, biopsies, etc.), with minimal distractions (talking, TV, etc.). Prior to each ECG, the patient should lie in a supine position in a calm environment for at least 5 minutes.

When performed in concert with serial PK collection on Cycle 1, Day 1 for Phase 1b dose levels 1 through 7, 2 ECGs will be performed pre-dose (within 1 hour of dose, separated by at least 15 minutes). Post-dose ECGs will be performed prior to and as close as possible to each PK sample collection at approximately maximum plasma concentration (maximum plasma concentration $[C_{max}]$; 1 and 2 hours), 4 hours, and 6 hours. If possible, patients should not consume additional food between dosing and the last ECG time point.

One set of triplicate 12-lead ECGs will be performed on Cycle 1, Day 1 at 2-hours post-dose for Phase 1b dose levels 8 through 13 and Phase 2. When performed in concert with serial PK collection on Cycle 2 Day 1 for these patients, 2 ECGs will be performed pre-dose (within 1 hour of dose, separated by at least 15 minutes). Post-dose ECGs will be performed prior to and as close as possible to each PK sample collection at approximately maximum plasma concentration (C_{max}; 1 and 2 hours), 3 hours, 4 hours, 5 hours, and 6 hours.

At screening and at the EOT visit, the ECG may be performed at any time during the clinic visit. ECGs may also be performed when clinically indicated, irrespective of the time of study drug dosing.

All ECGs will be independently reviewed by a central laboratory. Instructions for the collection and transmission of ECGs to the central ECG laboratory will be provided in the Study Manual.

Clinically significant abnormalities present at screening should be reported on the Medical History eCRF page. New or worsened clinically significant findings occurring after informed consent must be recorded on the Adverse Events eCRF page. All eligibility and patient management decisions should be based on the local reading of the ECG.

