- p. **12-Lead ECG** All ECGs will be performed in triplicate. Average corrected QT interval using Fridericia's method (QTcF) is to be calculated to confirm eligibility. ECGs will be performed in triplicate as follows: 2 ECGs will be performed in triplicate pre-dose within 1 hour of dosing at least 15 minutes apart. For Phase 1b (dose levels 1-7), post-dose ECGs will be performed prior to and as close as possible to PK blood draws at 1-, 2-, 4-, and 6-hours post-dose (±15 minutes) on Cycle 1 Day 1. For Phase 1b (dose levels 8-13) and Phase 2, one set of triplicate ECGs will be performed on Cycle 1 Day 1 at 2 hours post-dose and on Cycle 2 Day 1 prior to and as close as possible to the PK blood draws at 1-, 2-, 3-, 4-(pre-dose of second divided dose), 5-, and 6-hours post-dose (±15 minutes). Detailed instruction on ECGs is provided in Section 7.4.2.5.
- q. For patients in Phase 2 who are receiving nanatinostat, valganciclovir, and pembrolizumab, all AEs will be collected for up to and including 90 days after the last dose of study treatment or until the start of a new antineoplastic therapy, whichever is first; for all other patients, only serious adverse events (SAEs) will be collected during this safety follow-up time period.
- r. **EBV DNA**, **CMV**, **HIV levels** Plasma samples will be collected to investigate circulating EBV DNA, CMV, and HIV (HIV⁺ patients only). EBV DNA levels will be utilized for safety and biomarker analysis. For patients in Follow-up: If no relapse/disease progression, then patients will continue to have EBV DNA levels monitored every 12 weeks for up to 1 year from the date of the last dose of study drug during the follow-up period, until disease progression, start of new anti-cancer treatment, or end of study, whichever occurs first.

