3.4.2.3 Other Safety Variables

All 12-lead ECGs will be conducted in triplicate. Triplicate 12-lead ECGs will be performed separated by approximately 1 minute at screening, on Cycle 1 Day 1 (Phase 1b, all dose levels, and Phase 2), Cycle 2 Day 1 (Phase 1b dose levels 8 through 13 and Phase 2 only) and at the EOT visit. Prior to each ECG, the patient will lie in a supine position in a calm environment for at least 5 minutes.

When performed in concert with serial PK collection on Cycle 1 Day 1 (for Phase 1b dose levels 1 through 7), two ECGs will be performed pre-dose (within 1 hour of dose, separated by at least 15 minutes). Post-dose ECGs will be performed prior to and as close as possible to each PK sample collection at approximately maximum plasma concentration (1 and 2 hours), 4 hours, and 6 hours.

When performed in concert with serial PK collection on Cycle 1 Day 1 (for Phase 1b dose levels 8 through 13 and Phase 2), two ECGs will be performed pre-dose (within 1 hour of dose, separated by at least 15 minutes) and one set of triplicate 12-lead ECGs will be performed on Cycle 1 Day 1 at 2-hours post-dose. When performed in concert with serial PK collection on Cycle 2 Day 1 for these patients, two ECGs will be performed pre-dose (within 1 hour of dose, separated by at least 15 minutes). Post-dose ECGs will be performed prior to and as close as possible to each PK sample collection at approximately maximum plasma concentration (1 and 2 hours), 3 hours, 4 hours, 5 hours, and 6 hours.

At screening and at the EOT visit, the ECG may be performed at any time during the clinic visit. ECGs may also be performed when clinically indicated, irrespective of the time of study drug dosing.

Vital signs (temperature, blood pressure, and heart rate) will be collected at the screening visit (Day -28 to Day -1), on Day 1 of each cycle, and at the EOT visit. On visit days requiring serial PK collection, vital signs will be collected just prior to the first dose of valganciclovir and nanatinostat, and in concert and just prior to PK blood draws. On other indicated visit days, vital signs will be collected once (prior to dosing of study treatment if administered in clinic).

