4.1.4 Baseline Value

Unless otherwise noted, the baseline value will be defined as the last value reported prior to first dose of any study drug.

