4.6.5 Vital Signs, Physical Findings, and Other Observations Related to Safety

4.6.5.1 Vital Signs

Descriptive statistics for vital sign parameter measurements will be presented for results and change from baseline at each visit where parameters were scheduled to be collected.

4.6.5.2 12-Lead Electrocardiogram

Descriptive statistics will be presented for observed values and changes from baseline at each visit where parameters were scheduled to be collected. All 12-lead ECGs will be conducted in triplicate. The average of the triplicate ECG interval parameters will be summarized by treatment regimen.

Twelve-lead ECGs will be classified by the investigator as “normal,” “abnormal, not clinically significant,” or “abnormal, clinically significant.” The worst classification for each set of triplicate 12-lead ECGs will be used for analysis. Three-by-three contingency tables will be presented to summarize the shift from the baseline category to the worst post-baseline value. Summary results will include the count and percentage of patients within each shift category and treatment group.

Prolonged QTc intervals will be summarized as QTc measurements (msec) that are >450, >480, and >500 msec averaged over each set of triplicate 12-lead ECGs at each visit where ECG is routinely collected per the clinical study protocol. Change from baseline categories will also be summarized for measurements that represent a change >30 or >60 msec relative to the baseline value. Summary results will include the percentage of patients within each category and treatment group.

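### For dose levels 8 to 13 the documents disagree on whether a Cycle 1 Day 1 pre-dose ECG is taken, and the SAP does not say which ECG is then the QTc baseline

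*Protocol*

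**What the plan says.** Protocol Section 7.4.2.5 separates the dose levels. On Cycle 1 Day 1, "for Phase 1b dose levels 1 through 7, 2 ECGs will be performed pre-dose". For levels 8 to 13 the same section gives that day a single time point: "triplicate 12-lead ECGs will be performed on Cycle 1, Day 1 at 2-hours post-dose for Phase 1b dose levels 8 through 13". The two pre-dose ECGs for these levels appear only under Cycle 2 Day 1.

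Table 11 footnote p is attached to the screening, Cycle 1 Day 1, Cycle 2 Day 1 and end-of-treatment ECG cells. It opens with an instruction that names no dose level: "2 ECGs will be performed in triplicate pre-dose within 1 hour of dosing at least 15 minutes apart". It then gives post-dose times by dose level; for levels 8 to 13, "one set of triplicate ECGs will be performed on Cycle 1 Day 1 at 2 hours post-dose and on Cycle 2 Day 1". It closes by sending the site elsewhere: "Detailed instruction on ECGs is provided in Section 7.4.2.5".

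SAP 3.4.2.3 states that for levels 8 to 13 on Cycle 1 Day 1 "two ECGs will be performed pre-dose (within 1 hour of dose, separated by at least 15 minutes) and one set of triplicate" at 2 hours are done, under a lead-in that makes this conditional on serial PK collection that day.

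SAP 4.1.4 sets the general rule: "the baseline value will be defined as the last value reported prior to first dose of any study drug". SAP 4.6.5.2 averages within a triplicate set and summarises "measurements that represent a change >30 or >60 msec relative to the baseline value". It has no QTc-specific baseline and does not say how two pre-dose sets are combined.

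**The concern.** A change from baseline is only as good as the baseline. For levels 8 to 13, a site that took Section 7.4.2.5 as its detailed instruction would have no ECG shortly before first dose. The SAP rule would then reach back to screening, where the ECG may be done at any time during the visit. The QTc change and ECG shift summaries could thus rest on a same-day pre-dose reading for some patients and an older, untimed one for others, and the tables would not show which. The mix could differ by dose level, because only Section 7.4.2.5's text for levels 8 to 13 leaves out the pre-dose set.

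**Working it through.** **Step 1. Cycle 1 Day 1 pre-dose ECGs for levels 8 to 13, by source.**

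| Source | Pre-dose sets | Condition |
|---|---|---|
| Protocol 7.4.2.5 | 0 | none; only the 2-hour set is listed |
| Table 11 footnote p | 2 triplicate sets (2 × 3 = 6 tracings) | general wording, no dose level named |
| SAP 3.4.2.3 | 2 | when done with serial PK that day |

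**Step 2. Is the SAP's condition met?** Table 11 footnote s places PK sampling for levels 8 to 13 on Cycle 2 Day 1 only. No serial PK is scheduled on Cycle 1 Day 1, so the condition is never met. Read literally, the SAP sentence describes something that does not occur.

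**Step 3. Which ECG becomes baseline under SAP 4.1.4?** The Cycle 2 Day 1 pre-dose ECGs come after a 28-day Cycle 1 on drug and cannot serve. The outcomes are:
- Site followed footnote p: the second of two pre-dose sets, within 1 hour of dosing. The first set is unused.
- Site followed Section 7.4.2.5: the screening ECG, Day -28 to Day -1, unless an unscheduled pre-dose ECG exists. SAP 4.1.2 lets unscheduled values count towards baseline.

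The maximum age of the baseline is therefore 1 hour in the first case and 28 days in the second.

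**Step 4. What uses this baseline?** The ECG change-from-baseline statistics, the >30 and >60 msec categories and the shift tables in SAP 4.6.5.2. The >450, >480 and >500 msec categories use absolute values. No DLT criterion in Protocol 5.5.3.1 refers to QTc change, the QTc rows of Protocol Table 7 use absolute thresholds, and the RP2D definition in Protocol 5.5.2 does not mention QTc.

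**Step 5. What would averaging two pre-dose sets gain?** The documents give no QTc variability. Assume an independent SD s of 10 to 15 msec per triplicate set, no drug effect and a normal distribution.
- One-set baseline: SD of change = s√2, so P(change > 30) = P(Z > 30/(s√2)). For s = 10: 30/14.14 = 2.12, giving 1.7%. For s = 15: 30/21.21 = 1.41, giving 7.9%.
- Mean of two sets: SD of change = s√1.5. For s = 10: 30/12.25 = 2.45, giving 0.7%. For s = 15: 30/18.37 = 1.63, giving 5.1%.

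These are false-flag chances for one post-dose set. They measure the gain from averaging two sets. They are not a difference between dose levels: under SAP 4.1.4, levels 1 to 7 also use one set, the last. Any extra variation from a baseline days or weeks old is not in these figures and cannot be derived from the documents.

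**The case against.** The strongest reply is that the pre-dose ECGs are scheduled. Footnote p has one general pre-dose rule followed by post-dose times by dose level; it lists only post-dose times for levels 1 to 7 too, and nobody would conclude that those levels have no pre-dose ECG. Protocol Section 6 and the opening of Section 7 assign timing to Table 11. Section 7.4.2.5 is silent on the point and does not countermand the footnote. This largely stands, and it means the screening fallback arises only where a site followed Section 7.4.2.5 over Table 11. It does not remove the problem. Footnote p also marks the screening and end-of-treatment cells, where a pre-dose time has no meaning, so its opening sentence cannot apply to every cell that it marks. It also refers sites to the very section that omits the set.

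A reader might infer that baseline method is fully confounded with dose and schedule, so that a QT signal at the highest exposures would be obscured when the RP2D is chosen. The documents do not support this. Full confounding would need essentially every site at levels 8 to 13 to have skipped the footnote p sets, and nothing shows that. RP2D selection rests on DLTs, other safety data, PK, antitumor activity and plasma EBV DNA with the Safety Monitoring Committee; none of its stated rules uses QTc change from baseline.

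It is also fair to say that much is past repair. SAP 4.8 records that enrollment ended after the final Phase 1b level and that Phase 2 was not run, so new protocol wording cannot alter what was collected. The ECG analysis can still be specified.

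**Conclusion.** The inconsistency is real and of modest consequence. For levels 8 to 13, Section 7.4.2.5 omits a Cycle 1 Day 1 pre-dose ECG that footnote p and SAP 3.4.2.3 include, the SAP under a condition that is never met. SAP 4.8 lists the only changes from the protocol, and this difference is not among them. Depending on which text a site followed, the QTc baseline is at most 1 hour or up to 28 days old.

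On any reading, the last-value rule discards one of two sets where both exist. Under the assumed SD of 10 to 15 msec, averaging them would lower the chance of a false >30 msec flag from 1.7%–7.9% to 0.7%–5.1%. That is a precision gain, not evidence that levels 8 to 13 fare worse than levels 1 to 7.

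The effect is limited to descriptive change and shift summaries, in a study where SAP 4.1.1 rules out formal comparison of regimens. The conclusion assumes that patients were treated at levels 8 to 13; the documents do not say how many, nor how many of them lack a pre-dose ECG on the day of first dose.

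**What to change.** - Reconcile Protocol 7.4.2.5, Table 11 footnote p and SAP 3.4.2.3 so that they describe one Cycle 1 Day 1 ECG schedule for levels 8 to 13. Remove the serial-PK condition for that day from SAP 3.4.2.3. With enrollment closed, this can be a clarification in the SAP, listed in 4.8.
- In SAP 4.6.5.2, define QTc baseline as the mean of all Cycle 1 Day 1 pre-dose triplicate sets, using screening only if none exist, and flag those patients in the listings. A category cannot be averaged, so state a separate baseline rule for the shift table.
- Report, by dose level, how many patients have only a screening baseline.

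The cost is a few sentences in two SAP paragraphs, one entry in 4.8 and one count per dose level. No new data are needed. If the SAP can no longer be changed, its Section 1 already provides for documenting the departure in the clinical study report.
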